12. MEASUREMENT OF EFFECT

Although the clinical benefit of these drugs has not yet been established, the intent of offering this treatment is to provide a possible therapeutic benefit, and thus the patient will be carefully monitored for tumor response and symptom relief in addition to safety and tolerability. Patients with measurable disease will be assessed by standard criteria. For the purposes of this study, patients should be re-evaluated every 12 weeks.

12.1 Antitumor Effect – ISCL/USCLC/EORTC Response Criteria for Mycosis Fungoides and Sezary Syndrome

12.1.1 Definitions

Evaluable for Adverse Events. All patients will be evaluable for adverse event evaluation from the time of their first treatment.

Evaluable for Response. All patients who have received at least one cycle of therapy and have their disease re-evaluated will be considered evaluable for response (exceptions will be those who exhibit objective disease progression prior to the end of Cycle 1 who will also be considered evaluable). Patients on therapy for at least this period and who meet the other listed criteria will have their response classified according to the definitions set out below.

Response and progression will be evaluated in this study using the 2011 ISCL/USCLC/EORTC Response Criteria for Mycosis Fungoides and Sezary Syndrome (Olsen *et al.*, 2011).

12.1.2 Response and Evaluation Endpoints

The consensus response criteria for Mycosis Fungoides and Sezary Syndrome incorporates evaluation of skin, blood, lymph node, and visceral disease compartments.

Skin. Skin lesions and erythema will be evaluated using the mSWAT. During each mSWAT assessment, medical photography should be completed as described in Appendix F. Digital copies of the photographs will be retained at sites for quality assurance or secondary review purposes. The mSWAT is an objective, quantitative, severity-weighted method to assess the extent of skin lesions. An mSWAT score is derived by measuring each lesion as a percentage of total body surface area (%TBSA) and multiplying it by a severity-weighting factor (1 = patch, 2 = plaque, 4 = tumor). All individual numbers are then added to produce a total score. The mSWAT assessment tool is described in Appendix E.

Blood. Peripheral blood flow cytometry will be used to evaluate circulating malignant T-cells as indicated on the Study Calendar. Flow cytometry will be performed by each institution's standards.

Lymph nodes and Viscera. Either PET/CT or contrast-enhanced CT of the chest, abdomen, and pelvis (+/- neck as clinically indicated) may be used to evaluate response in lymph nodes and viscera. Investigators should utilize the same imaging modality performed for the baseline assessment throughout the trial. Although PET/CT may be utilized, response assessment is

NCI Protocol #: 10384

Version Date: September 5, 2023

performed through sum of the product of diameters for measureable lesions and therefore it is encouraged to also obtain a diagnostic CT along when PET imaging is performed.

The Investigator will identify, prospectively, the lesions to be followed to evaluate the subject's response to therapy. Lymph nodes must be > 15 mm in the long axis (greatest transverse diameter, GTD) or > 10 mm in the short axis if the GTD is > 10 to ≤ 15 mm. Lymph node biopsies may be performed, at the discretion of the Investigator, to rule out inflammation or to confirm disease. Analysis of these biopsies will be done by the pathologist at the study site.

12.1.3 Response Criteria

Response in each compartment will be assessed by the following criteria.

Response in Skin*

Complete response (CR)	100% clearance of skin lesions [#]
Partial response (PR)	50-99% clearance of skin disease from baseline without new tumors (T ₃) in subjects with T ₁ , T ₂ or T ₄ only skin disease
Stable disease (SD)	<25% increase to <50% clearance in skin disease from baseline without new tumors (T ₃) in subjects with T ₁ , T ₂ or T ₄ only skin disease
Progressive disease (PD) [†]	(1) >25% increase in skin disease from baseline or (2) New tumors (T ₃) in subjects with T ₁ , T ₂ or T ₄ only skin disease or (3) Loss of response: in those with CR or PR, increase of skin score of greater than the sum of nadir plus 50% baseline score
Relapse	Any disease recurrence in those with CR

*Based on mSWAT score.

A biopsy of normal appearing skin is unnecessary to assign a CR. However, a skin biopsy should be performed of a representative area of the skin if there is any question of residual disease where otherwise a CR would exist. If histologic features are suspicious or suggestive of Mycosis Fungoides/Sézary Syndrome (see histologic criteria for early MF7), the response should be considered a PR only.

[†]Whichever criterion occurs first.

Response in Blood*

CR*	B ₀
PR**	>50% decrease in quantitative measurements of blood tumor burden from baseline in those with high tumor burden at baseline (B ₂)
SD	Fails to attain criteria for CR, PR or PD
PD [†]	(1) B ₀ to B ₂ or (2) >50% increase from baseline and at least 5,000 neoplastic cells/ μ L or (3) Loss of response: in those with CR who were B ₁ or B ₂ at baseline, increase in neoplastic >1000 neoplastic cells/ μ L or in those with PR who were originally B ₂ at baseline, >50% increase from nadir and at least 5,000 neoplastic cells/ μ L
Relapse	Increase of neoplastic blood lymphocytes to \geq B ₁ in those with CR

* As determined by absolute numbers of neoplastic cells/uL.

NCI Protocol #: 10384

Version Date: September 5, 2023

** There is no PR in those with B1 disease at baseline as the difference within the range of neoplastic cells that define B1 is not considered significant and should not affect determination of global objective response.

† Whichever occurs first.

Response in Lymph Nodes*

CR	All lymph nodes are now <1.5 cm in greatest transverse (long axis) diameter by method used to assess lymph nodes at baseline or biopsy negative for lymphoma. In addition, lymph nodes that were N3 classification and <1.5 cm in long axis diameter at baseline, must now be <1 cm in diameter of the short axis or biopsy negative for lymphoma
PR	(1) Cumulative reduction >50% of the SPD [sum of the maximum linear dimension (major axis) x longest perpendicular dimension (minor axis) of each abnormal lymph node at baseline and no new lymph node >1.5 cm or >1.0 cm in the short axis if long axis 1-1.5cm diameter.
SD	Fails to attain the criteria for CR, PR and PD
PD [†]	(1) >50% increase in SPD from baseline of lymph nodes or (2) Any new node >1.5 cm in greatest transverse diameter or >1 cm in short axis diameter if 1-1.5 cm in long axis that is proven to be N3 histologically or (3) Loss of response: in those with PR or CR, >50% increase from nadir in SPD of lymph nodes
Relapse	Any new lymph node >1.5cm in long axis diameter in those with CR

* Peripheral and central lymph nodes.

† Whichever criterion occurs first.

Response in Viscera

CR	Liver or spleen or any organ considered involved at baseline should not be enlarged on physical exam and should be considered normal by imaging. No nodules should be present on imaging of liver or spleen. Any post treatment mass must be determined to be biopsy to be negative for lymphoma
PR	>50% regression in any splenic or liver nodules, or in measurable disease (SPD) in any organs abnormal at baseline. No increase in size of liver or spleen and no new sites of involvement.
SD	Fails to attain the criteria for CR, PR or PD
PD [†]	(1) >50% increase in size (SPD) of any organs involved at baseline or (2) New organ involvement or (3) Loss of response: in those with PR or CR, >50% increase from nadir in the size (SPD) of any previous organ involvement
Relapse	New organ involvement in those with CR

† Whichever criterion occurs first.

Global Response: The global response incorporates response assessments from all disease compartments.

Global Response Score

Global Score	Definition	Skin	Nodes	Blood	Viscera
CR	Complete disappearance of all clinical evidence of disease	CR	All categories have CR/NI		
PR	Regression of measurable disease	CR	All categories do not have a CR/NI and no category has a PD		
		PR	No category has a PD and if any other category involved at baseline, at least one has a CR or PR		
SD	Failure to attain CR, PR or PD representative of all disease	PR	No category has a PD and if any other category involved at baseline, no CR or PR in any		
		SD	CR/NI, PR, SD in any category and no category has a PD		
PD	Progressive disease	PD in any category			
Relapse	Recurrence disease in prior CR	Relapse in any category			

NI= noninvolved

12.1.4 Confirming early progression:

Immunotherapeutics may result in infiltration of immune cells leading to transient increase in the size in malignant lesions, or undetectable lesions becoming detectable. In cutaneous lymphoma this may manifest as worsening appearance of skin lesions or lymph nodes early in treatment. To allow sufficient time to differentiate such pseudoprogression from true progression, patients with early progression events may continue on treatment with increased surveillance until true progression is confirmed. Treatment beyond progression in such cases can occur at the investigator's discretion after approval by the Principal Investigator.

Skin progression: Patients with progression in the skin compartment documented any time up to, and including, their assessment at 12 weeks may continue on treatment if they meet all of the following criteria:

1. Progression cannot be due to development of new tumors (T3) disease in a patient with T1, T2, or T4 disease
2. Patients must have monthly mSWAT assessments while continuing treatment
3. During this period of unconfirmed progression, the mSWAT score on each subsequent assessment must be less than or equal to the most recent mSWAT score (i.e. the mSWAT must improve with each subsequent evaluation)

It is strongly encouraged that a skin biopsy be performed if the investigator suspects pseudoprogression in the skin. The patient may continue with monthly mSWAT examinations until Cycle 6. By Cycle 6, the patient must meet criteria for stable disease or better to continue on treatment. If progression is confirmed by an increase in mSWAT in a subsequent evaluation, then the date of progression for endpoint analysis will be the first date of progression, not the

NCI Protocol #: 10384
Version Date: September 5, 2023
date of the confirmation.

Lymph node: Patients with progression in the lymph node compartment documented on their first scheduled assessment at 12 weeks may continue on treatment if they meet the following criteria:

1. Either a biopsy must be performed of a progressing lymph node (preferred), or a repeat scan must be performed in 4-8 weeks after the week 12 scan showing progression
2. If a biopsy is performed on a progressing lesion, it must show changes consistent with pseudoprogression.
3. If a biopsy cannot be performed, then a subsequent scan performed 4-8 weeks later must have an SPD less than or equal to the week 12 scan. If progression was due to the appearance of new assessable lymph nodes, all new lymph nodes must be equal or smaller in cross-sectional area to their measurements on the week 12 scan

If a follow up scan performed 4-8 weeks later shows improvement, then the patient can continue on the treatment protocol until the next planned assessment at Cycle 6. All patients must have a lymph node response of SD or better on their Cycle 6 imaging assessment to continue on treatment protocol.

If progression is confirmed by imaging evaluation on either the scan performed 4-8 weeks later or their Cycle 6 imaging, then the date of progression for endpoint analysis will be the first date of progression, not the date of the confirmation scan.

If the repeat evaluations do not confirm progression, the patient will continue to be treated and evaluated as per the original study calendar.

12.2 Definitions of Study Endpoints

Overall Response Rate (ORR): ORR is defined as the proportion of patients who have a partial or complete response to therapy as defined by the global response score.

Duration of Response (DOR): DOR is defined as the duration of overall response is measured from the time measurement criteria are met for CR or PR (whichever is first recorded) until the first date that recurrence or PD is objectively documented.

Overall Response Rate 4 (ORR4): ORR4 is defined as the proportion of patients who have a partial or complete response to therapy AND a duration of response \geq 4 months.

Overall Response Rate 6 (ORR6): ORR6 is defined as the proportion of patients who have a partial or complete response to therapy AND a duration of response \geq 6 months.

Overall Response Rate 12 (ORR12): ORR12 is defined as the proportion of patients who have a partial or complete response to therapy AND a duration of response \geq 12 months.

Progression-Free Survival (PFS): PFS is defined as the duration of time from start of treatment to time of progression or death, whichever occurs first.

Time to next treatment (TTNT): TTNT is defined as the duration of time from the start of treatment on this protocol to time of the next anti-neoplastic therapy.

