Q2W = Every 2 weeks, IV = Intravenous

Phase 2 Design:

The phase 1b portion has been completed and the phase 2 portion of the protocol is now open.. There was one DLT identified in the phase 1b portion of the trial with 6 patients treated at dose Level 1. Therefore, the recommended phase 2 dose (RP2D) was established as **Level 1 (30mg/kg magrolimab starting cycle 1)**. The phase 2 portion will be a two-arm, randomized, open-label design. This cohort will seek to determine whether Hu5F9-G4 (magrolimab) plus

mogamulizumab will have improved efficacy as compared to mogamulizumab alone. We will enroll 82 patients with relapsed or refractory mycosis fungoides (MF) / Sézary Syndrome (SS). Patients will be randomized 1:1 to either Hu5F9-G4 (magrolimab) plus mogamulizumab or mogamulizumab alone. Randomization will be stratified by 2 characteristics: 1) Disease type (MF vs SS) and 2) Stage (1B-2A vs 2B-IV). To encourage accrual and to better assess the added effect of Hu5F9-G4 (magrolimab), the trial will allow for one-way crossover from the mogamulizumab only arm to the combination arm. Crossover will be allowed for patients with progressive disease or stable disease lasting 6 months. While not typically a criterion for crossover in other cancers, prolonged stable disease has not been an acceptable outcome for this patient population due to the presence of symptoms associated with ongoing disease.

TABLE OF CONTENTS

SCHEMA	3
1. OBJECTIVES	9
1.1 Primary Objectives.....	9
1.2 Secondary Objectives.....	9
1.3 Exploratory Objectives	9
2. BACKGROUND	9
2.1 Study Diseases	9
2.2 CTEP IND Agent.....	11
2.3 Other Agent.....	15
2.4 Rationale	16
2.5 Correlative Studies Background	20
3. PATIENT SELECTION	24
3.1 Eligibility Criteria	24
3.2 Exclusion Criteria	26
3.3 Inclusion of Women and Minorities	28
4. REGISTRATION PROCEDURES	28
4.1 Investigator and Research Associate Registration with CTEP	28
4.2 Site Registration.....	29
4.3 Patient Registration.....	32
4.4 General Guidelines.....	34
5. BIOMARKER, CORRELATIVE, AND SPECIAL STUDIES	34
5.1 Summary Table for Specimen Collection.....	34
5.2 Specimen Procurement Kits and Scheduling.....	36
5.3 Specimen Tracking System Instructions.....	36
5.4 Specimen Collection	40
5.5 Shipping Specimens from Clinical Site to the EET Biobank	42
5.6 Biomarker Plan	45
5.7 Integrated Correlative Studies.....	51
5.8 Exploratory/Ancillary Correlative Studies	51
6. TREATMENT PLAN	55
6.1 Agent Administration.....	55

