1. OBJECTIVES

1.1 Primary Objectives

1.1.1 Phase 1

1.1.1.1 To characterize the safety and toxicity profile and to determine a safe recommended phase 2 dose (RP2D) of Hu5F9-G4 (magrolimab) when given in combination with mogamulizumab

1.1.2 Phase 2

1.1.2.1 To compare the proportion of patients who achieve a partial or complete response lasting at least 6 months (ORR6) of the combination of Hu5F9-G4 (magrolimab) and mogamulizumab versus mogamulizumab alone

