2.4.5 Rationale for the primary endpoint in the primary phase 2 cohort

CTCL has unique symptoms, including disturbing visible and pruritic qualities that impact treatment decisions, complicating traditional trial endpoints, including ORR, PFS, and DOR. Objective responses with >50% reduction may not equal clinical benefit, and symptomatic patients often elect to transition to new therapy without objective progression, censoring them from PFS and DOR analysis. Meaningful impact of CTCL therapy should reflect both ORR and DOR without the initiation of new treatment. Therefore, composite endpoints that reflect both ORR and DOR are increasingly being explored in trials of CTCL (Kim *et al.*, 2016). In this trial, we have selected the primary endpoint of ORR6, defined as the rate of objective responses lasting at least 6 months without the initiation of new therapy. Importantly, this new type of composite endpoint has been well-received by the FDA as a relevant endpoint for trials in CTCL. ORR4 (the rate of objective responses lasting at least 4 months without the initiation of new therapy) was the primary endpoint of the pivotal ALCANZA trial which lead to the FDA approval of brentuximab vedotin for the treatment of CD30-positive cutaneous T- cell lymphomas (Prince *et al.*, 2017). We believe that for this patient population, which differs from that of the ALCANZA trial, a response duration of 6 months would be more clinically meaningful and important than the shorter ORR4 endpoint.

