
Q2W = Every 2 weeks, IV = Intravenous
**Priming dose will be given over 3 hours (+/- 30 minutes)*
***Hu5F9-G4 (magrolimab) to be administered before mogamulizumab on days when both treatments are given*
**** Within 24 hours prior to each of the first 2 doses of Hu5F9-G4 infusion, patients must have a documented hemoglobin level of ≥ 9 g/dL. Patients who do not meet these criteria must be transfused and have their hemoglobin rechecked to meet the minimum hemoglobin threshold prior to administering each of the first 2 doses of Hu5F9-G4. An additional hemoglobin must be checked 3 to 6 hours after the initiation of the first and second doses of Hu5F9-G4. The patient should be transfused as clinically appropriate. Investigators should consider additional hemoglobin monitoring during the first week of treatment in patients with symptoms of anemia or at increased risk for complications of anemia.*

Table 4: Regimen Description for Phase 2 (Mogamulizumab Only Arm)

Regimen Description					
Agent	Premedication; Precautions	Dose	Route	Schedule	Cycle Length
Mogamulizumab	650-1,000 mg acetaminophen oral (PO) and 25 mg diphenhydramine	1 mg/kg	IV	Weekly for cycle 1, then Q2W starting from cycle 2	28 days (4 weeks)

	(PO or IV) or a comparable regimen at least 15 minutes before the first dose of mogamulizumab.				
Q2W = Every 2 weeks, IV = Intravenous					

For patients who crossover to the Hu5F9-G4 (magrolimab)/mogamulizumab combination due to progression or lack of response after 6 months, no washout will be required and treatment will proceed with an identical schedule as the combination arm starting with the priming dose of Hu5F9-G4 (magrolimab).

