6.6 Cross-over

6.6.1 Eligibility for cross-over:

Subjects randomized to the mogamulizumab-only arm will be eligible to cross-over to the combination arm of Hu5F9-G4 (magrolimab) and mogamulizumab if they meet EITHER of the following criteria:

1. Have received at least 2 full treatment cycles of mogamulizumab and meet global criteria for progression of disease
2. Have received at least 6 full treatment cycles of mogamulizumab and meet global criteria for stable disease

Additionally, to be eligible for cross-over, subjects must meet BOTH of the following criteria:

1. Meet the eligibility criteria at the time of cross-over. The only exception to the eligibility criteria will be that subjects who have active large cell transformation (LCT) at the time of cross-over will be eligible for cross-over.
2. Subjects must also have a skin biopsy performed within 4 weeks prior to cross-over with a pathologic diagnosis confirming cutaneous lymphoma. It is strongly recommended to perform molecular studies of TCR clonality if there is ambiguity in the diagnosis. This criteria is to exclude the possibility of progression incorrectly being attributed to a mogamulizumab-associated rash.

Subjects will have 4 weeks from the date of progression to meet eligibility for cross-over.

6.6.2 Procedures related to cross-over:

Subjects who cross-over to the combination therapy arm will adhere to the study calendar. The following procedures do not need to be repeated at baseline if performed within 4 weeks of cross-over:

- Imaging
- Flow cytometry
- Skin biopsies
- Correlative blood collection

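### The endpoint section drops the no-new-therapy condition from ORR6, and nothing says how a control patient's response after crossover is scored

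*Combined protocol and SAP*

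**What the plan says.** All references are to the combined protocol and SAP.

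- **Section 2.4.5** explains the choice of ORR6, "defined as the rate of objective responses lasting at least 6 months without the initiation of new therapy". It notes that symptomatic patients often change treatment without objective progression. It describes ORR4 with the same condition.
- **Section 12.2**, the endpoint definitions, says: "ORR6 is defined as the proportion of patients who have a partial or complete response to therapy AND a duration of response" of at least 6 months. Duration of response runs "until the first date that recurrence or PD is objectively documented". Starting another therapy is not an end event.
- **Section 1.1.2** compares the proportion with a response "lasting at least 6 months (ORR6) of the combination of Hu5F9-G4 (magrolimab) and mogamulizumab versus mogamulizumab alone". It also has no new-therapy condition.
- **Schema, Phase 2 Design:** "the trial will allow for one-way crossover from the mogamulizumab only arm to the combination arm". Under 6.6.1 one route is progression after at least 2 cycles. The other needs no progression: "Have received at least 6 full treatment cycles of mogamulizumab and meet global criteria for stable disease".
- **Section 6.1** describes patients who cross over "due to progression or lack of response after 6 months, no washout will be required".
- **Section 9.1, Analysis Plan**, includes everyone who begins treatment and makes patients without an assessment failures.
- **Section 9.5.2** makes categories 4 to 9 failures. Stable disease is category 3.
- **Section 6.5** ends follow-up at the next significant treatment, while **6.6.2** keeps crossed-over patients on the study calendar.

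**The concern.** The primary endpoint has two definitions that can classify the same patient differently. The clearest case is a control patient with stable disease after 6 cycles who crosses over without progression and then responds for at least 6 months on the combination. Under 12.2 as written, that patient has a qualifying response and counts as a success for mogamulizumab alone. Under 2.4.5 the patient fails, but only if crossover is new therapy, which is not stated.

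Plain ORR has the same gap ("ORR is defined as the proportion of patients who have a partial or complete response to therapy as defined by the global response score"), as do ORR4 and ORR12. Crossover at progression is less exposed, because 9.5.2 already makes that category a failure.

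The trial is open-label, crossover is planned, and the futility rule in 9.1 uses the same ORR6. If the scoring is not written down beforehand, it will be chosen by people who may already have seen outcomes. Crediting these responses to control would make an effective combination look less effective.

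**Working it through.** **Inputs from 9.1 (Phase 2 Power and Sample Size).** 41 patients per arm; control ORR6 of 30% in SS and 10% in MF, with MF 70% of the trial; odds ratio 3.2; Cochran-Mantel-Haenszel test over 4 strata; one-sided alpha 0.15; stated power 86%. Section 9.2 gives accrual of 4 per month. Section 12 gives evaluation every 12 weeks.

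**Assumed.** Stage splits each disease type about equally, giving 12 SS (6+6) and 29 MF (14+15) per arm. No continuity correction.

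**Step 1: the plan's own figure.**
- Combination rate = 3.2p / (1 − p + 3.2p). SS: 0.96/1.66 = 57.8%. MF: 0.32/1.22 = 26.2%. Overall: (12 × 0.578 + 29 × 0.262)/41 = 35.5%.
- Control: (12 × 0.30 + 29 × 0.10)/41 = 6.5/41 = 15.9%. Expected control failures: 41 − 6.5 = 34.5.
- Power over 400,000 simulated trials is 87.0%, and the asymptotic formula gives 86.7%. The stated 86% reproduces.

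**Step 2: effect per credited patient.** Exactly k control failures, drawn at random, are recoded as successes.

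| k | Power | One-sided false-positive rate (odds ratio 1) |
|---|---|---|
| 0 | 87.0% | 0.152 |
| 1 | 79.8% | 0.083 |
| 2 | 70.3% | 0.042 |

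**Step 3: effect at assumed rates.** Let x be the share of control failures who cross at stable disease and then respond for 6 months. For example, 10% crossing × 10% responding gives x = 1%, and 30% × 20% gives 6%. Each control rate p becomes p + x(1 − p).

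| x | Patients (34.5x) | Control ORR6 | Power | False-positive rate |
|---|---|---|---|---|
| 1% | 0.3 | 16.7% | 84.7% | 0.128 |
| 3% | 1.0 | 18.4% | 78.7% | 0.091 |
| 6% | 2.1 | 20.9% | 68.6% | 0.052 |

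**Step 4: the futility look.**
- A success after stable-disease crossover takes 24 weeks of control treatment, 1 week of priming, 12 weeks to a documented response (assumed from the evaluation interval) and 6 months of duration. That is 37 weeks (8.5 months) + 6 = 14.5 months, or 15.4 if crossing takes 4 more weeks.
- The 41st patient enrols at 41/4 = month 10.25. If evaluable means 12 weeks plus 6 months (assumed), the look falls near month 19.0.
- Patients enrolled early enough number between 4 × (19.0 − 15.4) ≈ 14 and 4 × (19.0 − 14.5) = 18 of 41, so at most about 44%.
- With 20 per arm (6 SS, 14 MF), the chance that the combination's count of successes is no higher than control's, at a true odds ratio of 3.2, follows from exact binomial sums. Control rates are contaminated by 0.44x, or by the full x as a ceiling.

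| x | 44% observed | All observed (ceiling) |
|---|---|---|
| 0 | 9.1% | 9.1% |
| 1% | 9.7% | 10.4% |
| 3% | 10.9% | 13.3% |
| 6% | 12.8% | 18.3% |

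**The case against.** The best reply is that the intent is clear once the sections are read together. Section 2.4.5 is worded as a definition, and nothing in 12.2 expressly admits responses after new therapy. An objective such as 1.1.2 is normally abbreviated. Section 6.1 already calls stable-disease crossover a lack of response. Section 6.6 re-checks eligibility and refers to a baseline at crossover, and 6.1 restarts the combination schedule from priming, so the post-crossover period looks like a separate course. Outside therapy is barred by 6.1 and 6.3, and follow-up ends at the next significant treatment. A stable-disease patient is in no ORR numerator unless the category is later upgraded. The contamination rates are all assumed, and at x = 1% the effect is small.

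Much of this stands as evidence of intent, and off-protocol therapy is the lesser part of the problem. What remains is that no section states the rule. Section 2.4.5 settles crossover only if crossover is new therapy. Section 6.5 governs follow-up, not scoring, and 6.6.2 keeps these patients under assessment. Section 9.5.2 does not say whether a category fixed before crossover may be upgraded after it. The point about magnitude is fair: the per-patient figures show sensitivity and do not predict how many patients would be affected.

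**Conclusion.** The concern holds. The two statements of the primary endpoint differ on a condition that decides who is a responder. The literal 12.2 rule would credit a combination response to the control arm after stable-disease crossover.

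The loss is about 7 points of power for the first patient credited and about 17 points for two. At the assumed x of 1% to 6%, power is about 85% to 69%, and the futility look is affected less. These sizes rest on assumed crossover and response rates and an assumed even stage split. The bias cannot favour the combination or inflate false positives, and the sample-size calculation is sound for an uncontaminated control arm. This should be fixed, but it does not undermine the design.

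**What to change.** 1. **Section 12.2.** Define ORR, ORR4, ORR6 and ORR12 as a global PR or CR first documented on the randomised regimen, before crossover or any other new anti-lymphoma therapy. For ORR4, ORR6 and ORR12 add that the response must last at least 4, 6 or 12 months without PD, recurrence, death, crossover or new anti-lymphoma therapy. Patients with any of these first are non-responders in their randomised arm.
2. State that protocol crossover counts as new therapy for these endpoints.
3. State openly that first documentation on the randomised regimen, and death as failure, go beyond 2.4.5.
4. **Section 6.5.** State that crossover closes the randomised-arm response endpoints while data collection under 6.6.2 continues.
5. **Sections 1.1.2 and 9.1** (Analysis Plan and futility rule). Cite the 12.2 definition.
6. Report post-crossover responses separately and descriptively.

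The cost is wording in four sections, settled before outcome data are seen. No new data or patients are needed, and the criteria for crossing over do not change. Reported response rates may be slightly lower.
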